### **Data monitoring board**

An independent data monitoring committee belonging to the Central Ethics Committee of Children's Hospital of Chongqing Medical University has been established for the trial. This committee will perform interim data analysis, investigate compliance with the trial and monitor adverse events. Formal interim analyses of efficacy will be carried out by the DMB when 25%, 50% and 75% of the outcome data were available. The board will advise the principal investigator who will remain the only responsible for the trial conduction and for any eventual decision to stop or continue it.

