### **Randomization**

Neonates will be randomised and assigned either to NCPAP or NHFOV arms with a 1:1 ratio, when patients fulfil all inclusion criteria. Simple randomisation will be done according to a computer-generated random number table and will be posted in a

specific secured website available on 24/7. Twins will all be allocated in the same treatment group. Infants randomised to one arm cannot crossover to the other or vice-versa during the study.

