### **Sample size calculation**

According to the results of our last multicentre study, the risk of failure while receiving NCPAP for very preterm infants with RDS was 30%, and a reduction of 20% for babies receiving NHFOV. We decide to aim a difference of 15% in the rate of the respiratory support failure. Considering an alpha error of 0.05 and a power of 90%, 170 neonates would be needed in each group.

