### **Statistical methods**

Outcomes will be analysed on an intention-to-treat basis. We will calculate a risk difference (with 95%CI) for dichotomous outcomes and mean (with 95%CI) or median (25–75th percentile, using Hodges-Lehmann) differences for continuous outcomes between the study groups. Continuous variables will be compared using

Student's t test or the Mann-Whitney rank sum test as appropriate. Categorical variables were compared using the  $\chi^2$  test. P values  $< 0.05$  were considered statistically significant.

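### Three formal efficacy interims and a final test have no stopping boundary or adjusted final level, so the claimed 5% type I error is not protected (about 12.6% to 12.8% if P<0.05 is applied at every look)

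*Combined protocol and SAP*

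**What the plan says.** The Data monitoring board section schedules three looks at efficacy before the end of the trial: "Formal interim analyses of efficacy will be carried out by the DMB when 25%, 50% and 75% of the outcome data were available". It does not limit them to safety or describe them as descriptive. Stopping is contemplated: the board advises the principal investigator, "who will remain the only responsible for the trial conduction and for any eventual decision to stop or continue it". No numerical rule is attached to the advice or to the decision.

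The Sample size calculation section makes a single claim about error: "Considering an alpha error of 0.05 and a power of 90%, 170 neonates would be needed in each group". It does not mention interim looks.

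The Statistical methods section names the test ("Categorical variables were compared using the" chi-square test) and gives one threshold: P values below 0.05 "were considered statistically significant". It does not say whether that threshold applies at the interims, whether the final level is adjusted for them, or whether the chi-square test is continuity-corrected. No other section supplies these points, and no charter or other governing document is mentioned.

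**The concern.** Each extra look at accumulating data at an unadjusted level is another chance of a false positive. With four looks and no rule, the claimed 5% holds only if the interims can never produce an efficacy stop or claim, or if they use a very strict threshold. The plan states neither.

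Three things are at stake.

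- **The error rate of the primary comparison.** If an interim result can end the trial or support a claim, the unadjusted P value and 95% CI do not have their nominal properties.
- **The size of the reported effect.** A small early sample reaches P<0.05 only when the observed difference is large, so an early stop on that criterion overstates the benefit of NHFOV.
- **Credibility.** The stop or continue decision rests with one person and has no numerical rule. A boundary written after interim results have been seen cannot repair this.

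**Working it through.** **Inputs**

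- NCPAP failure rate: "the risk of failure while receiving NCPAP for very preterm infants with RDS was 30"% (Sample size calculation).
- Target difference: "We decide to aim a difference of 15% in the rate of the respiratory support failure" (same section), read as 30% against 15%.
- Alpha 0.05, power 90%, 170 per group (same section). Sidedness is not stated; two-sided is assumed.
- Allocation: "Neonates will be randomised and assigned either to NCPAP or NHFOV arms with a 1:1 ratio" (Randomization).
- Looks at fractions 0.25, 0.50, 0.75 and 1 of the data (Data monitoring board), about 42, 85, 127 and 170 infants per arm.

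**Step 1. The plan's sample size.** With pooled rate 0.225, the two-sided formula is

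n = [1.960·√(2·0.225·0.775) + 1.2816·√(0.30·0.70 + 0.15·0.85)]² / 0.15² = (1.157 + 0.745)² / 0.0225 ≈ 160.8, so 161 per arm.

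The continuity correction gives (160.8/4)·[1 + √(1 + 4/(160.8·0.15))]² ≈ 173.9, so 174. The stated 170 is within 3% of 174. One-sided versions give 131 and 144, which supports the two-sided reading. All of these are single-look calculations.

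**Step 2. Four looks at |z|>1.96, no true difference.** The four test statistics are jointly normal with correlation √(t_j/t_k) between looks j<k: 0.707 between looks 1 and 2, and 0.5 between looks 1 and 4. The probability of at least one crossing is:

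| After look | 1 | 2 | 3 | 4 |
|---|---|---|---|---|
| Cumulative type I error | 5.0% | 8.3% | 10.7% | 12.6% |

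**Step 3. The same with the actual test.** Binomial simulation, one million trials, 30% failure in both arms:

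| Unstated rule | Uncorrected chi-square | Corrected |
|---|---|---|
| Final test only | 5.0% | 3.8% |
| P<0.05 at all four looks, any crossing acted on | 12.8% | 8.7% |
| O'Brien-Fleming boundary | 5.0% | 3.7% |

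At common failure rates of 15% to 25%, the uncorrected four-look figure is about 12.9% to 13.0%. By normal theory, P<0.001 at the three interims with P<0.05 at the end gives 5.1%. These figures count crossings in both directions; by symmetry, false findings in favour of NHFOV are half, 12.8%/2 = 6.4% against a nominal 2.5%.

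**Step 4. The first look when the true rates are 30% and 15%.** With 42 per arm and a pooled rate of 22.5%, the observed difference must exceed about 1.96·√(2·0.225·0.775/42) = 1.96·0.0911 ≈ 17.9 points to reach P<0.05. That is already more than the true 15. The chance of crossing is about 38.6%, and the mean estimated difference in trials that cross is 23.8 points. With the correction, these are about 27% and 25.8 points.

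**Step 5. Boundaries that hold 5%.** Classic O'Brien-Fleming sets |z| > C/√t with C = 2.024 for four equally spaced looks:

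| Fraction of data | 0.25 | 0.50 | 0.75 | 1 |
|---|---|---|---|---|
| Critical \|z\| | 4.05 | 2.86 | 2.34 | 2.02 |
| Nominal P | 0.00005 | 0.004 | 0.019 | 0.043 |

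The Lan-DeMets O'Brien-Fleming-type spending function gives 4.33, 2.96, 2.36 and 2.01 at the planned times (nominal P about 0.000015, 0.003, 0.018 and 0.044).

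**Step 6. Cost in power at 170 per arm, 30% against 15%.** Uncorrected test: 92.0% for a single final test, about 91.2% with O'Brien-Fleming. Corrected test: 89.6% and 88.9%. In sample size terms, O'Brien-Fleming inflates the requirement by a factor of 1.022 (161 to 165, or 174 to 178 per arm). A Pocock boundary (P<0.0182 at every look) inflates it by 1.183 (161 to 191, or 174 to 206).

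**The case against.** The strongest reply is that the inflation is conditional. The plan does not say that P<0.05 applies at the interims. The board only advises, and no crossing triggers anything automatically. If the interims never lead to an efficacy stop or claim, the final test keeps its level. Across the rules and test versions the plan leaves open, the error runs from about 5% or slightly below to about 13%, so 12.8% is the figure for one rule and not a prediction.

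That is correct, and the figures above must be read that way. The first-look estimates are conditional in the same sense. But the objection does not supply the missing rule. The looks are called formal efficacy analyses, a stop is contemplated, and P<0.05 is the only threshold given, so the four-look reading is one the text permits. An advised stop based on an efficacy result is still a data-dependent stop.

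Two narrower objections also stand. The version of the chi-square test does not cause the problem: either version holds alpha below or at about 5% under a proper boundary, and the choice is the sponsor's. The power margin is also thin. The plan makes no allowance for loss or for twins allocated together. With an assumed 5% loss (about 161 per arm), the uncorrected final test at |z|>2.025 has 89.2% power, and the full sequential design is slightly higher, at about 90% or just under.

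**Conclusion.** The concern holds. The plan commits to three formal efficacy analyses and claims an overall alpha of 0.05, but contains nothing that secures it. The two-sided type I error for the primary outcome is 5.0% if no interim can lead to an efficacy stop or claim, 5.1% with P<0.001 at the interims, and 12.6% to 12.8% if P<0.05 is applied at all four looks and any crossing is acted on. With a continuity-corrected test the last figure is 8.7%.

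These results assume two-sided testing, 170 independent infants per arm, looks at the planned fractions and a 30% common failure rate. The omission itself rests on none of these assumptions. It must be fixed before the first look, because it affects the primary conclusion and cannot be credibly repaired once interim results are known.

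**What to change.** Before the first interim, amend Data monitoring board and Statistical methods in one of two ways.

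1. **If an efficacy stop is possible:** prespecify one boundary for the primary outcome that holds overall two-sided alpha at 0.05. One example is classic O'Brien-Fleming with the critical values in Step 5 and the final analysis tested at 0.043. If the looks may not fall exactly on the planned fractions, use the Lan-DeMets O'Brien-Fleming-type spending function and recompute the bounds at the actual times. State whether the boundary binds the stop or continue decision, and how the risk difference and its CI will be reported after sequential testing.
2. **If no efficacy stop is intended:** say that the interims cannot lead to an efficacy stop or claim. The final test can then stay at 0.05.

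In either case, state that testing is two-sided and whether the chi-square test is continuity-corrected, and mention the looks in Sample size calculation.

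The cost is wording, plus about 0.7 points of power under option 1. With the uncorrected test, 170 per arm still exceeds the 165 needed for 90% power, provided there is no loss and no correlation between twins. With the corrected test, power is already just under 90% (89.6%) before any adjustment and falls to 88.9%. Option 2 costs no power.

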### **Ethics and dissemination**

The study protocol was approved by the Ethics Committee of Children's Hospital of Chongqing Medical University (n.2019.161) and registered in the ClinicalTrials.gov registry (ID: NCT05141435). The trial was performed in accordance with the approved guidelines and regulations of the participating institutions. Informed consent will be obtained antenatally or on NICU admission from parents or guardians. Hospitals participating in the study will share the findings and results of the study, which will be presented at national conferences and peer-reviewed paediatrics journals
